This study builds on that clinical collection and review of PROMs by nurses. We propose a prospective pilot study to describe the proportion of patients with a change in their physician's assessment of their overall toxicity burden that result from routine physician review of PROMs during radiotherapy. We hypothesize that routine physician review of PROMs during on-treatment visits will (1) increase proportion of patients with an increased in their physician's assessment of their overall toxicity burden during definitive radiotherapy, and (2) correspondingly increase the proportion of patients receiving physician-directed interventions for treatment-related symptoms.

**Figure 1:** Patient PROM completion rates in the thoracic radiation oncology clinic

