**7. Study Statistics**

This is a prospective pilot study.

- a. Primary outcome variable(s).

*The primary outcome is the proportion of patients with any change in their physician-assessed burden scores for at least one on-treatment visit, along with their exact binomial 95% confidence interval.*

- b. Secondary outcome variables

*The secondary outcome is the proportion of patients with a change in their on-treatment management for at least one on-treatment visit, along with the exact binomial 95% confidence interval.*

- c. Exploratory outcome variables:

We will also summarize the mean change in the physician-assessed burden score across on-treatment-visits, and across patients, using mean, standard deviation, median and ranges. We will report the distribution of changes (an increase, decrease or no change) in physician burden score after PROM review across all visits.

We will also summarize the mean change in the physician interventions across on-treatment-visits, and across patients, using mean, standard deviation, median and range of cumulative changes in interventions made. We will explore the average cumulative number of management interventions based on each specified numerical change in burden score.

*Additionally, we will describe differences in mean physician burden score between first half and second half of treatment.* To describe changes in the physician perception of treatment-related toxicity resulting from routine physician review of PROMs, we also will compare the mean change in burden scores for on-treatment visits 4 to 7 to the mean change in burden scores for visits 1 to 3. Treatment-related toxicities are expected to worsen over time. If PROM review does not change physician perception of treatment-related symptoms, there would no difference between the mean change in burden score across patients in the first half of treatment compared to the second half of treatments. Using paired t-tests, we will examine the differences between mean physician burden score across patients in the second compared to the first half of the treatments. We would expect the changes in burden scores to be greater in later visits since treatment-related toxicities and corresponding PROMS are expected to worsen over time.

*Depending on the proportion of patients with a change in physician burden assessment, we will also explore potential variables associated with a change in burden assessment by the physician.*

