We will evaluate associations between variables of interest and development of any point as well  $\geq 2$  absolute point change in their physician's assessed burden scores for at least one on-treatment visit using Fisher's exact test. Variables may include but are not limited to: PROM question type from the corresponding on-treatment visit (symptom type, symptom severity, most bothersome symptom, interference on activity of daily living), baseline clinical or demographic information, and/or treatment information including treating-physician or disease-site. We will not adjust for multiple comparison due to the exploratory nature of this study.

d. Statistical plan including sample size justification and interim data analysis.

The analyses will be descriptive. The statistical plan is written by study objective above. Exploratory plots will be made (line graph, bar plots) and used to visualize the distribution of data of interest. These plots may include but are not limited to cumulative number of additional interventions recommended with time and the distribution of type of additional interventions (counseling, medications/interventions, referrals, testing/evaluation). Exploratory tables will compare the average burden score change with the average cumulative number of management interventions per week. Secondary analysis will explore ratings on the Clinician Feedback Form.

Annually, 60-80 lung and esophageal cancer patients and 20 gastrointestinal tumors are treated with definitive RT over the course of 5-7 weeks at Johns Hopkins. On average  $>80\%$  of on-treatment visits have PROMs completed for lung cancer patients. A sample size of at least 50 patients yields a two-sided 95% confidence interval with a width of less than 30% for descriptive analyses. Thus, we would be able to estimate the proportion of patients with a change in their physician assessed burden score and change in management with a margin of error of 15 % ( $\pm 15\%$ ).

There will be no interim data analysis.

e. Early stopping rules.

Not applicable.

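### The exploratory association tests ignore the direction of re-rating, so they cannot separate upward from downward correction and can miss an ordered variable whose levels act in opposite directions

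*Combined protocol and SAP*

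**What the plan says.** All references are to the combined protocol and SAP.

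- **Association tests (section 7c).** The plan states "We will evaluate associations between variables of interest and development of any point as well" as a change of at least 2 points, the latter being an "absolute point change in their physician's assessed burden scores for at least one on-treatment visit using Fisher's exact test". Both outcomes are yes/no per patient and neither has a direction.
- **Candidate variables (section 7c).** These include "PROM question type from the corresponding on-treatment visit (symptom type, symptom severity, most bothersome symptom, interference on activity of daily living", together with baseline, demographic and treatment variables, treating physician and disease site.
- **Multiplicity (section 7c).** "We will not adjust for multiple comparison due to the exploratory nature of this study".
- **Primary outcome (section 7a).** The "proportion of patients with any change in their physician-assessed burden scores for at least one on-treatment visit", which is also sign-free.
- **Direction elsewhere (section 7c).** "We will report the distribution of changes (an increase, decrease or no change) in physician burden score after PROM review across all visits". The mean change in score is also summarised across visits and patients, and compared between visits 1 to 3 and visits 4 to 7. None of these summaries is broken down by the candidate variables.
- **Hypothesis (end of section 3, Background).** Physician review of PROMs is expected to "increase proportion of patients with an increased in their physician's assessment of their overall toxicity burden during definitive radiotherapy".

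**The concern.** The hypothesis is directional: physicians are thought to under-recognise symptoms, and PROM review should raise their ratings. The association analysis is where the plan asks which PROM, baseline or treatment variables go with a re-rating, yet it counts an upward and a downward correction as the same event.

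Two things follow. First, even a clear association would not say whether the variable marks patients whose burden was under-rated or patients whose burden was over-rated. Second, severity and interference are ordered. If high levels pull the rating up and low levels pull it down, both groups count as changed and the contrast between them shrinks. A result of no association for severity could then be carried into the randomised study that section 4f foresees, although severity did drive the re-rating.

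**Working it through.** **The plan's own figure.** The plan gives no power for the association tests. Its one sample-size figure is a 95% interval narrower than 30% with 50 patients. The exact binomial interval at 25/50 runs from 35.5% to 64.5%, a width of 28.9%, so the figure reproduces. It does not bear on this point.

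**Inputs from the documents.** At least 50 patients; radiotherapy over 5 to 7 weeks with weekly visits; outcome defined as a change at one or more visits; Fisher's exact test.

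**Assumptions, none of them in the documents.** An even split of 25 high v 25 low; 6 visits per patient; each patient's level fixed over the visits; visits independent; two-sided 5% level; and the per-visit chances of a rise (r) and a fall (f) shown below.

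**Formulas.**
- Ever changed = 1 − (1 − r − f)^6
- Ever increased = 1 − (1 − r)^6
- Power = sum of the binomial probabilities of all 25 v 25 tables with Fisher p ≤ 0.05

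For case 1, ever changed is 1 − 0.83^6 = 67% (high) v 1 − 0.85^6 = 62% (low). Ever increased is 1 − 0.85^6 = 62% v 1 − 0.97^6 = 17%.

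| Case | High r / f | Low r / f | Falls as share of all changes | Ever changed | Power, sign-free | Ever increased | Power, rises |
|---|---|---|---|---|---|---|---|
| 1 | 15% / 2% | 3% / 12% | 14/32 = 44% | 67% v 62% | 4% | 62% v 17% | 90% |
| 2 | 15% / 2% | 3% / 6% | 8/26 = 31% | 67% v 43% | 34% | 62% v 17% | 90% |
| 3 | 15% / 2% | 3% / 2% | 4/22 = 18% | 67% v 26% | 80% | 62% v 17% | 90% |
| 4 | 15% / 2% | 3% / 1% | 3/21 = 14% | 67% v 22% | 89% | 62% v 17% | 90% |
| 5 | 15% / 2% | 3% / 0% | 2/20 = 10% | 67% v 17% | 95% | 62% v 17% | 90% |
| 6 | 15% / 5% | 3% / 2% | 7/25 = 28% | 74% v 26% | 91% | 62% v 17% | 90% |
| 7 | 12% / 6% | 3% / 2% | 8/23 = 35% | 70% v 26% | 85% | 54% v 17% | 72% |
| 8 | 10% / 10% | 3% / 3% | 13/26 = 50% | 74% v 31% | 84% | 47% v 17% | 53% |

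**Reading the table.** The loss is severe when falls concentrate in the low group (cases 1 and 2). It is modest when falls are equally frequent in both groups (case 3). It is negligible or reversed when falls are more frequent in the high group (cases 4 to 8). The overall share of falls does not decide it: case 8 has the largest share, and there the sign-free test is clearly better.

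**The same contrast in single tables of 25 v 25.**
- Opposite levels act in opposite directions (10 up, 2 down v 2 up, 10 down): sign-free 12/25 v 12/25, p = 1.00; rises 10/25 v 2/25, p = 0.018.
- Both movements occur within one group (8 up, 8 down v 2 up, 2 down): sign-free 16/25 v 4/25, p = 0.0012; rises 8/25 v 2/25, p = 0.074.

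**The case against.** The strongest reply is that the choice is coherent. The primary objective and outcome concern any change, and the exploration tests variables against that same event. The tests are exploratory, unadjusted and conditional on how many patients show a change. The signed scores are collected, so a split could be added later. The unfavourable cases are also assumed: case 1 needs low-level patients to be re-rated downward four times as often as upward. The protocol's premise is under-reporting by physicians, and the scale starts at 0, so scores near zero have little room to fall. All of this stands. It limits the weight, but it does not give the tests a direction.

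Three stronger readings are tempting, and the documents support none of them.

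- A reader might infer that a variable which raises some patients' scores and lowers others' will go undetected. When both movements occur among patients at the same level, both count as a change and the sign-free test picks the variable up (p = 0.0012 above). Cancellation of that kind affects a signed mean.
- A reader might infer that the plan discards direction apart from one frequency table. Section 7c also has the mean changes overall and by half of treatment, and nothing there makes them absolute. What is missing is direction by candidate variable.
- A reader might infer that rise-only outcomes should replace the sign-free ones. Cases 5 to 8 show that this could lose power.

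**Conclusion.** The point holds in a limited form. That the association outcomes carry no sign, and that no planned analysis relates direction to the candidate variables, follows from the text and needs no assumption. The tests as written therefore cannot address the study's own directional hypothesis.

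The loss of power is conditional. It arises for an ordered variable when rises gather at high levels and falls at low levels, and it ranges from large (4% v 90%) to modest (80% v 90%) under the assumed rates. Other plausible patterns make the sign-free test as good or better. Because the documents give no rates of rises or falls, the size for this trial cannot be stated. The weight is low: no primary or secondary result rests on these tests.

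**What to change.** In section 7c, keep the two sign-free outcomes, which match the primary outcome. Add, as further Fisher outcomes for the same variables, any increase and an increase of at least 2 points after PROM review at one or more visits and, separately, any decrease at one or more visits. A patient with both a rise and a fall at different visits would count under both.

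This takes one sentence. The ratings before and after review are already recorded at each visit (section 4a), so no new data or patients are needed. The downside is three more outcomes per variable in an analysis already declared unadjusted, so the report should show all of them and not only those that reach significance.

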As a part of the study, treating physicians over-seeing the care of their patients will be asked to provide a global burden score. Lee et al. demonstrated the feasibility of using a global burden score to capture the provider's overall perception of the combined burden of *all* assessed symptoms, using a visual analogue scale demarcating an aggregate score from 0 to 10. This scale uses anchors at 0, 2, 4, 6, 8, and 10 for no, mild, moderate, severe, life-threatening adverse events, and death, respectively.

\*\* During weekly on-treatment visits and prior to reviewing their patient's PROMs, physicians will rate the symptom burden for each of their patients from 0 to 10 using available clinical data. Routine available clinical data include: vital signs, laboratory work, physical exam, nursing assessment, physician's clinical judgement. Then after reviewing the patient's PROMs, physicians will re-rate the patient's symptom burden and report any change in recommended interventions due to review of the PROMs. Management changes include (1) additional counseling, (2) medications/interventions changed, (3) referrals to other services, and (4) further testing/evaluation (**Appendix B**). At the end of each patient's course of radiotherapy, providers will complete a Clinician Feedback Form to answer questions regarding the impact of PROM review on overall symptom perception and management during treatment (**Appendix C**). These forms were designed to be easy to complete and will take an estimated 5 minutes per patient.

\*\*At the time of enrollment, research staff will collect pertinent patient baseline and characteristics through clinical chart review. During each on-treatment visit, research staff collect pertinent clinical and treatment variables through chart review (**Appendix D**). The research staff, if available on site, will also be available to assist patients in completing the questionnaires during scheduled visits and to address any issues or concerns patients have in completing the questionnaires.

\*\* Marks demarcates interventions that will/may require research staff availability and assistance.

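### Section 7c names only Fisher's exact test for associations; it ignores the order of severity and interference scores and loses power if the effect is a gradient (minor)

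*Combined protocol and SAP*

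**What the plan says.** Section 7c plans to relate variables of interest to two yes/no outcomes per patient: any change, and an absolute change of at least 2 points, in the physician's burden score. Both are assessed "for at least one on-treatment visit using Fisher's exact test". No rank, trend or regression method is named for these associations.

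The list of candidate variables includes "symptom severity, most bothersome symptom, interference on activity of daily living), baseline clinical or demographic information, and/or treatment information", which spans two groups:
- PROM items: "PROM question type from the corresponding on-treatment visit (symptom type, symptom severity, most bothersome symptom, interference on activity of daily living".
- Other variables: "baseline clinical or demographic information, and/or treatment information including treating-physician or disease-site".

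The list is open-ended, and the section says that multiplicity will not be adjusted for. The second group is fed by the chart review in section 4, where "research staff will collect pertinent patient baseline and characteristics through clinical chart review". The text gives no rule for grouping ordered or continuous variables.

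Section 7d calls the analyses descriptive. Its only design figure is for precision: "A sample size of at least 50 patients yields a two-sided 95% confidence interval with a width of less than 30% for descriptive analyses". No power is claimed for any association.

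**The concern.** Fisher's exact test compares groups as if their labels could be shuffled. That suits disease site or treating physician. For symptom severity or interference it sets aside the fact that the levels run from less to more. A continuous variable can enter only after it has been cut into groups. With the cut-point left open, two outcomes and no multiplicity adjustment, the cut is one more route to a chance finding.

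The protocol's own reasoning points to a gradient. Section 7c expects larger score changes at later visits because symptoms and PROMs worsen over time, which implies that worse PROMs go with more change. With about 50 patients, a test that ignores order may miss such a pattern. What is at stake is the pilot's ability to show which patients' PROMs alter the physician's view. The headline proportions are not at stake.

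**Working it through.** **1. The plan's own figure.** For 25 of 50 patients, the widest case, the exact binomial 95% interval is 35.5% to 64.5%: width 28.9 points, half-width 14.5. This agrees with the stated width below 30% and "with a margin of error of 15" percent. Nothing below alters it.

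**2. The named variables.** Six are named. Two are ordered (symptom severity, interference). Four are unordered (symptom type, most bothersome symptom, treating physician, disease site). Any continuous variable would come from the open baseline and treatment classes.

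**3. Inputs.** From the documents: 50 patients, a binary outcome per patient, Fisher's exact test. Assumed, because the documents are silent: two-sided 5% level per test; 3 to 5 ordered levels; 30 to 85% of patients changed; odds ratio (OR) 1.5 to 2.5 per level.

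**4. Formulas.** Let level j hold c_j patients, of whom a_j changed, with m changed in total and n = 50.
- Model: logit(p_j) = α + j·ln(OR), with α set to give the assumed overall share changed.
- Probability of a table with these margins: P = ∏C(c_j, a_j) / C(n, m).
- Fisher p-value: sum of P over all tables no more probable than the one observed.
- Exact rank-sum (trend) p-value: with T = Σ r_j·a_j and r_j the midrank of level j, sum of P over all tables with |T − m(n+1)/2| at least as large as observed.

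**5. What the assumed effect means.** Take level shares of 15/25/25/20/15%, OR 2 and 50% changed. The chance of a change is then about 21, 34, 51, 68 and 81% across the levels (0.15×0.21 + 0.25×0.34 + 0.25×0.51 + 0.20×0.68 + 0.15×0.81 = 0.50). The top-to-bottom odds ratio is 2⁴ = 16; at OR 1.5 it is 1.5⁴ ≈ 5.1. Even the weaker setting is a strong gradient.

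**6. Simulated power, five levels.**

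| Level shares | Changed | OR per level | Fisher | Exact trend | Gap (points) |
|---|---|---|---|---|---|
| 15/25/25/20/15% | 50% | 1.5 | 24% | 43% | 19 |
| 15/25/25/20/15% | 50% | 2 | 61% | 82% | 21 |
| 15/25/25/20/15% | 30% | 2 | 54% | 76% | 22 |
| Even | 50% | 1.5 | 28% | 47% | 19 |
| Even | 50% | 2 | 72% | 89% | 17 |
| Even | 70% | 2 | 60% | 81% | 21 |
| Skewed | 50% | 2 | 49% | 71% | 22 |
| Skewed | 70% | 2 | 29% | 57% | 28 |

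At 80% changed and OR 2, a further run gave 36% against 62%, a gap of 26. Over OR 1.5 to 2 and 30 to 80% changed, the gap is about 10 to 27 points. The 28 in the table is within simulation error, since each power in the even and skewed rows has a standard error of about 2 points. Widening to OR 2.5 and 85% changed gives about 7 to 32. Under no effect, both tests reject in about 5% of trials or fewer.

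**7. Fewer levels, and continuous variables.** The gap is about 6 to 19 points with four levels and 0 to 11 with three. For a continuous predictor cut at its median, Fisher loses about 14 to 37 points to the rank-sum test (for example 42% against 65%). The median cut is also an assumption.

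**8. Where the result reverses.** With a U-shape over five even levels (chance of change 80, 50, 20, 50, 80%), Fisher has 74% power and the trend test 3%. With a peak in the middle it is 76% against 4%. With four unordered physicians it is 80% against 8%.

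**The case against.** The strongest reply is that Fisher's test is a defensible choice here. It is valid in sparse tables at this sample size, suits four of the six named variables, and detects patterns that a trend test misses. A U-shape is a live possibility because the outcome has no direction: low PROM scores could prompt downward re-rating and high scores upward re-rating, and both count as a change. The gradient in the simulations is therefore an assumption that favours the trend test. The analyses are also exploratory, conditional on how many patients change, and carry no power claim.

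All of this stands, and it limits the point without removing it. The reversal for unordered variables does not count against a fix that keeps Fisher's test for them. The U-shape is a real cost, so Fisher's result should stay as a supporting check. Exploratory status lowers the importance, but the plan still intends to test these associations.

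A reader might infer that most of the listed variables are ordered or continuous, or that the plan discards the order of age and dose. The documents do not support either: two of the six named variables are ordered, and age and dose are not named. Nor do they support saying that Fisher's test brings no benefit.

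**Conclusion.** The point holds in a limited form. For severity, interference and any continuous baseline or treatment variable, the one named test ignores order and would lose power against a steady gradient: about 10 to 27 points with five levels under the stated assumptions, and as little as none with three. A reader might take a single figure such as 15 to 20 points as the loss. The documents cannot support one, because they give no event rate, effect size, number of levels or significance level for these tests.

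The primary and secondary proportions, their intervals and the sample size do not change. This is a minor, inexpensive improvement to an exploratory analysis.

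**What to change.** Amend section 7c along these lines:

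- Unordered variables (symptom type, most bothersome symptom, treating physician, disease site): Fisher's exact test, as now.
- Ordered or continuous variables: exact Wilcoxon rank-sum (trend) test on the uncategorised value, with an odds ratio per level or unit and 95% confidence interval from exact or penalised logistic regression. The regression must be named, because a rank test does not itself give an odds ratio.
- PROM items: one value per patient, defined the same way whether or not the score changed, for example the worst value over the completed visits. The present wording ties the item to the corresponding visit, and a patient whose score never changed has no such visit. If the worst value is used, report the number of completed visits too, since more visits raise both the worst value and the chance of a change.
- For each ordered variable, show the proportion changed by level and report Fisher's result as a supporting check. State in advance that the trend result is the main one, so that two p-values do not become a choice.

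The cost is a few sentences and no new data. The downside is that the rank or trend test has little power for a U-shaped effect, which the display by level and the supporting Fisher result are there to catch.

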##### Clinician Recruitment:

The treating radiation oncologists have expressed a willingness to participate in the study and will help with patient recruitment. The radiation oncologists will be recruited at Johns Hopkins and at WellSpan Health through emails and will have differing levels of experience. Once we have received IRB approval, we will go through a formal consenting process. Physicians will have the option to decide not to participate. If a physician is willing to participate, she/he will be asked to provide written informed consent.

A participating physician may be included a co-investigator in this study. No physician co-investigator may analyze their own patient's PROM data included as a part of the study. There is no requirement that to be a co-investigator physician must also be a research participant.

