- b. If your study involves data/biospecimens from participants enrolled under other research studies with a written consent or under a waiver of consent, please list the IRB application numbers for those studies. Please note: Certificate of Confidentiality (CoC) protections applied to the data in source studies funded by NIH or CDC will extend to this new study if the funding was active in 2016. If this situation applies, Section 36, question 4 in the application will need to be answered "Yes" and "Hopkins Faculty" should be selected in question 7. No other documents are required.

Not applicable.

- c. Study duration and number of study visits required of research participants.

Patients will be enrolled in the study prior to or on their first radiotherapy on-treatment visit and will continue through the course of their radiotherapy. Data will be collected at routine weekly on-treatment visits; no study-specific visits are required

d. Blinding, including justification for blinding or not blinding the trial, if applicable.

Blinding will not be possible as the treating physician will need to provide routine care to the patients enrolled on this study. In addition, the treating physician will need to appropriately assign burden scores, and to report on whether there was a change in management for each of their patients who enroll on this study.

e. Justification of why participants will not receive routine care or will have current therapy stopped.

Patients will continue to receive their routine care. This study will not alter nor stop the planned radiotherapy treatments. All patients enrolled will undergo routine weekly on-treatment evaluation and toxicity management by the treating physician.

f. Justification for inclusion of a placebo or non-treatment group.

There is NO placebo group. This is a pilot study to evaluate whether physician review of PROMs during radiotherapy changes the physician's assessment of a cancer patient's overall toxicity burden and management of treatment-related symptoms. There is insufficient sample size to include a placebo group. In future studies building on this, where we have a greater sample size, we can randomize patients to 2 arms: with and without routine PROM review.

g. Definition of treatment failure or participant removal criteria.

Patients will be removed if they desire to refrain from answering the PROM questionnaire.

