**Radiation Oncologists**

**Inclusion criteria:**

- Must be the physician overseeing the care of the patient who answers the PROMS

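### The exploratory disease-site test is not stratified by treating physician, who supplies both burden ratings, so a site association could reflect the rater

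*Combined protocol and SAP*

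**What the plan says.** Section 7c relates candidate variables to two outcomes, any change and a change of at least 2 points. The second is described as an "absolute point change in their physician's assessed burden scores for at least one on-treatment visit using Fisher's exact test". The candidate list is open-ended and includes "treatment information including treating-physician or disease-site". Neither section 7c nor 7d mentions stratification, a multivariable model or a physician random effect. Multiplicity adjustment is expressly declined because the work is exploratory.

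The outcome comes from the physician. Under Study Procedures, "treating physicians over-seeing the care of their patients will be asked to provide a global burden score", and after reading the PROMs "physicians will re-rate the patient's symptom burden and report any change in recommended interventions due to review of the PROMs". Section 4d (Blinding) confirms that "the treating physician will need to appropriately assign burden scores". Section 5 ties rater to patient: a participating radiation oncologist "Must be the physician overseeing the care of the patient who answers the PROMS".

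On who the raters are, Clinician Recruitment says: "The radiation oncologists will be recruited at Johns Hopkins and at WellSpan Health through emails and will have differing levels of experience". Their number and the disease sites each one treats are not given. The nearest evidence on specialisation is the caption of Figure 1 in the Background, "Patient PROM completion rates in the thoracic radiation oncology clinic".

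**The concern.** A physician who often revises a score after reading PROMs produces many patients with a change; one who rarely revises produces few. If those two physicians see different disease sites, their patients' proportions differ even when disease site has no bearing on the outcome. Testing physician and site in separate two-way tables does not resolve this. Both tests may be positive, and nothing in the plan would show which variable carries the association. Enrolling more patients per physician does not help either, because the source is the small number of raters.

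At stake is how an exploratory finding is read. A reported difference between, say, thoracic and gastrointestinal patients would invite a clinical explanation when it might only describe two raters.

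**Working it through.** **The plan's own figure.** Section 7d says at least 50 patients give a 95% interval narrower than 30 percentage points. The exact binomial interval is widest at 25 of 50: 35.53% to 64.47%, a width of 28.9 points. The figure reproduces, and the concern here does not bear on it.

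**Inputs from the documents.** Fisher's exact test (7c); at least 50 patients (7d); 60–80 lung and oesophageal to 20 gastrointestinal patients a year at Johns Hopkins (7d). That ratio is 60/80 = 75% to 80/100 = 80% thoracic, or about 38 to 40 of 50 if accrual follows it.

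**Assumptions.** The number of physicians, their rates of changing a score, and the concentration of each physician on one site. There is no true site effect in any false-positive calculation.

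**Check 1: two physicians with partial overlap (exact enumeration, 40/10 split).** Let physician A's patients show a change with probability pA = 0.3 and physician B's with pB = 0.7, and let a share s of each site's patients see that site's main physician. Then:

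- thoracic rate = s·pA + (1 − s)·pB
- gastrointestinal rate = (1 − s)·pA + s·pB

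At s = 0.8 these are 0.8×0.3 + 0.2×0.7 = 0.38 and 0.2×0.3 + 0.8×0.7 = 0.62. The last column is a Cochran-Mantel-Haenszel (CMH) test stratified by physician, by simulation.

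| s | Rates by site | Fisher rejects | CMH rejects |
|---|---|---|---|
| 0.5 | 0.50 / 0.50 | 2.9% | not run |
| 0.7 | 0.42 / 0.58 | 10.0% | 4.7% |
| 0.8 | 0.38 / 0.62 | 20.6% | 4.8% |
| 0.9 | 0.34 / 0.66 | 36.7% | 4.2% |
| 1.0 | 0.30 / 0.70 | 56.7% | not estimable |

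With a milder contrast (0.4 against 0.7) at s = 0.8, Fisher rejects 11.9%.

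**Check 2: several physicians, each treating one site only (simulation).** Each physician's log-odds of a patient showing a change is Normal with mean 0 (a 50% rate) and the SD shown. One SD either side of the mean is 27–73% at SD 1. Patients are split 25/25, with half the physicians at each site. Ranges are across repeated runs.

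| Physicians | SD 1 | SD 0.5 | SD 0 |
|---|---|---|---|
| 4 | 23–25% | about 10% | 3–4% |
| 6 | 16–17% | 7–10% | 3–4% |
| 10 | 10–11% | about 6% | about 3% |

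**Check 3: less favourable to the concern.**

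- With a 40/10 split and six physicians as 4+2, SD 1 gives 11.8% and SD 0.5 gives 5.5%.
- In that setting with an average change rate of 80%, the figures are 10.6% and 4.8%; at 90% they are 6.7% and 3.5%.
- With 3+1 physicians, SD 1 and a 50% rate, the figure is still 22%.

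Inflation therefore needs two things together: raters who differ, and raters aligned with site. It shrinks as the number of raters grows.

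**The case against.** The strongest reply is that the decisive premise is undocumented. Nothing assigns physicians to disease sites, and a figure caption is thin evidence of specialisation. If patients are evenly spread, there is no inflation. This stands, and it is why the point is conditional.

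The tests are also exploratory and optional, and whether they are run depends on the observed proportion with a change. Treating physician is already on the list, so a physician effect would be visible beside a site effect, and the open list leaves room for centre. That limits the consequence but does not remove the problem: a separate test of physician does not adjust the test of site, and the exploratory label answers multiplicity, not confounding.

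Three stronger readings are tempting, and the documents do not support them:

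- **Lung and oesophageal patients are rated by different physicians.** Section 7d counts these two groups together and gives no reason to think so.
- **Thoracic physicians already have experience of PROM review that others lack.** The Background describes routine collection with review by nurses, not prior physician review.
- **A site signal would decide whom the later randomised study enrols.** Section 4f says only that a future study could randomise with or without PROM review. It does not mention selecting sites.

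**Conclusion.** The point holds in conditional form. As written, 7c cannot separate a disease-site association from the habits of the physicians who produce the score. Under full nesting and no true site effect, false site signals occur about 10–25% of the time at physician SD 1 with 4 to 10 physicians, and about 5–10% at SD 0.5. Without rater variation, or with patients evenly spread, the rate stays near 3–4%. These figures rest on assumed rater variation, physician numbers and allocation; a high overall rate of change would lower them.

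A reader might infer that the headline results are compromised. They are not: the primary and secondary proportions involve no comparison between sites, so this confounding does not reach them. Severity is low; this is a worthwhile refinement of an exploratory analysis.

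**What to change.** Add to section 7c:

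1. Cross-tabulate treating physician, by code, against disease site and centre.
2. Report the disease-site association with an exact or CMH test stratified by physician, beside the planned unstratified Fisher test.
3. Where physicians do not overlap across sites, state that site, centre and physician effects cannot be separated, and draw no site conclusion.

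The change is confined to the site association; the other candidate variables need not be stratified on this account. Physicians are consented participants and section 8d promises summary reports without identifying information, so any per-physician figures should be de-identified. With few raters, a code alone may not be enough.

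The cost is a few sentences and a little analysis on data already collected. Stratifying loses some power for the site test: in one illustration with two physicians and 80% concentration, under assumed rates, it fell from about 44% to 35%. The stratified association may also prove not estimable, in which case reporting that is the right outcome.
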